6.5.2.7. Status of Menstruation Recovery

If the first menstruation after the end of study treatment administration is observed before the Safety Follow-up visit, the date of onset of the first menstruation is recorded in the electronic case report form (eCRF). Patients whose menses has not resumed as of the Safety Follow-up visit for whom there is no explanation for the lack of resumption (e.g., medical procedure or medications) will be contacted again by telephone 3 (\pm 0.5) months after the Safety Follow-up visit to determine if menses has resumed and will be asked about factors that may affect resumption of menses.

If the patient enrolls directly into another relugolix clinical study upon completion of the Week 104 visit, follow-up under this protocol to determine the status of menstruation recovery may not be required.

7. SAFETY CONSIDERATIONS

Study assessments of safety include adverse events, physical examinations, vital signs (and weight), clinical laboratory tests, ECGs, and bone mineral density assessments.

7.1. Adverse Event Definitions

7.1.1. Adverse Event

Adverse event: An adverse event is any unfavorable and unintended sign (including an abnormal laboratory finding), symptom, or disease (new or exacerbated) temporally associated with the use of a medicinal product, whether or not related to the medicinal product.

Events meeting the definition of an adverse event include:

- A worsening, excluding minor fluctuations, in the nature, severity, frequency, or duration of a pre-existing condition;
- Development of an intercurrent illness during the study;
- Development of symptoms that may or may not be related to the use of a concomitant medication or investigational product;
- Injury or accidents: If a medical condition is known to have caused the injury or accident, the medical condition and the accident should be reported as 2 separate medical events (e.g., for a fall secondary to dizziness, both "dizziness" and "fall" should be recorded separately); and

- An investigational abnormality (e.g., laboratory parameter, vital sign, ECG) only if the abnormality is considered clinically significant by the investigator based on at least one of the following criteria:
 - o Induces clinical signs or symptoms;
 - o Requires active intervention;
 - o Requires interruption or discontinuation of study drug.

Events that do not meet the definition of an adverse event include:

- Medical or surgical procedures (e.g., surgery, endoscopy, tooth extraction, transfusion); the condition that leads to the procedure is an adverse event;
- Pre-existing diseases or conditions present or detected before the start of study drug administration that do not worsen;
- Situations where an untoward medical event has not occurred (e.g., planned hospitalization for an elective procedure, with elective defined as known or planned at the time of signing of the informed consent);
- Events of heavy menstrual bleeding, as heavy menstrual bleeding is quantified as an efficacy endpoint, unless meets seriousness criteria.

Adverse events that occur during the study should be evaluated by the investigator and graded according to Common Terminology Criteria for Adverse Events (CTCAE). Episodic adverse events, such as vomiting, or those that occur repeatedly over a period of consecutive days are "intermittent". All other events are "continuous". Additional information on detecting, documenting, and reporting adverse events and serious adverse events are provided below. No toxicity-related dose reductions of study drug are permitted; however, study drug can be held for a period of up to 2 weeks for evaluation and treatment of an adverse event. The study drug may be restarted if deemed safe for the patient by the investigator.

7.1.2. Serious Adverse Event

A serious adverse event is any untoward medical occurrence that, at any dose:

- a. Results in death;
- b. Is life-threatening;

NOTE: The term "life-threatening" in the definition of "serious" refers to an event in which the study participant was at risk of death at the time of the event. It does not refer to an event which hypothetically might have caused death if it were more severe. For example, druginduced hepatitis that resolved without evidence of hepatic failure would not be considered life-threatening even though drug-induced hepatitis can be fatal.

c. Requires hospitalization or prolongation of existing hospitalization;

NOTE: In general, hospitalization signifies that the patient has been admitted to a hospital, independent of the duration of that hospitalization. Complications that occur during hospitalization are adverse events. If a complication prolongs hospitalization or fulfills any other serious criteria, the event is serious. When in doubt as to whether "hospitalization" occurred or was necessary, the adverse event should be considered serious. Hospitalization

for elective treatment of a pre-existing condition that did not worsen from the Week 52/Baseline visit is not considered an adverse event.

d. Results in persistent or significant disability/incapacity;

NOTE: The term disability means a substantial disruption of a person's ability to conduct normal life functions. This definition is not intended to include experiences of relatively minor medical significance such as uncomplicated headache, nausea, vomiting, diarrhea, influenza, and accidental trauma (e.g., sprained ankle), which may interfere or prevent everyday life functions but do not constitute a substantial disruption.

- e. Is a congenital anomaly/birth defect;
- f. Important medical events that jeopardize the patient and may require medical or surgical intervention to prevent one of the outcomes listed above. Examples of such events are invasive or malignant cancers, intensive treatment in an emergency room or at home for allergic bronchospasm, blood dyscrasias or convulsions that do not result in hospitalization, or development of drug dependency or drug abuse.

7.2. Adverse Event Reporting

The reporting of serious adverse events by the sponsor (Myovant Sciences GmbH) to regulatory authorities is a requirement and each authority has a timetable for reporting these events based upon established criteria. Likewise, it is the responsibility of the investigator to report serious adverse events to their local institutional review board (IRB) or institutional ethics committee (IEC).

Care will be taken not to introduce bias when detecting adverse events and/or serious adverse events. Open-ended and non-leading verbal questioning of the patient is the preferred method to inquire about adverse event occurrence. Appropriate questions include:

- "How are you feeling?"
- "Have you had any (other) medical problems since your last visit/contact?"
- "Have you taken any new medicines, other than those provided in this study, since your last visit/contact?"

The patient's answers to study questionnaires will not be used as a primary means to collect adverse events, however they should be reviewed by the study site personnel and the study monitors. Should the investigator or site staff become aware of a potential adverse event through the information collected with these instruments, proper follow-up with the patient for medical evaluation should be undertaken. Through this follow-up, if it is determined that an adverse event not previously reported has been identified, normal reporting requirements should be applied.

All patients who experience an adverse event will be evaluated at appropriate time intervals until the event resolves or has stabilized or become chronic. At the conclusion of the study, the investigator and medical monitor will assess unresolved adverse events and determine if additional follow-up is warranted.

All adverse events, whether related to the study drug treatment, must be fully and completely documented on the adverse event case report form and in the patient's source documents. In

addition, any adverse event resulting in permanent treatment discontinuation must be recorded on the appropriate case report form as well as documented in the patient's source documents. Adverse event terms should include a diagnosis, as available, in preference to listing the individual signs and symptoms. If the diagnosis is not known, the investigator should record each sign and symptom as an individual adverse event.

Overdose and pregnancy in the patient will be reported as described in Section 7.7 and Section 7.8, respectively.

7.2.1. **Adverse Event Reporting Period**

Adverse events and serious adverse events will be collected under this extension study protocol from the administration of the first dose of extension study drug until the Safety Follow-up visit approximately 30 days after the last dose of study drug or the date of initiation of another investigational agent or hormonal therapy affecting the hypothalamic-pituitary-gonadal axis or surgical intervention for uterine fibroids, whichever occurs first, as also specified in the study Schedule of Activities (Table 1-1). Serious adverse events reported to the investigator after the safety reporting period should be reported to the sponsor if the investigator assesses the event as related to the study drug treatment.

Reporting instructions for serious adverse events are provided in Section 7.6.

7.3. **Assigning Causal Relationship to Study Drug**

The reasonable possibility of the relationship of an adverse event to study drug(s) is to be assessed with careful medical consideration at the time of evaluation of an adverse event. The following definitions are to be used for the relationship of the adverse event to study drug:

- **Probably related**: A clinical event, including laboratory test abnormality, with a reasonable time sequence to administration of the drug, unlikely attributed to concurrent disease or other drugs or chemicals, and that follows a clinically reasonable response on readministration (rechallenge) or withdrawal (dechallenge).
- Possibly related: A clinical event, including laboratory test abnormality, with a reasonable time sequence to administration of the drug but that could also be explained by concurrent disease or other drugs or chemicals. Information on drug withdrawal may be lacking or unclear.
- Not related: A clinical event, including laboratory test abnormality, with a temporal relationship to drug administration that makes a causal relationship improbable and/or in which other drugs, chemicals, or underlying disease provide a plausible explanation.

All adverse events, whether related to study drug, must be fully and completely documented on the adverse event page of the eCRF and in the patient's clinical record. In the event a patient is withdrawn from the study because of an adverse event, it must be recorded on the eCRF as such.

7.4. **Assigning Severity Rating for Adverse Events**

Severity describes the intensity of a specific event (as in mild, moderate, or severe myocardial infarction); the event itself, however, may be of relatively minor medical significance, such as a severe headache. This is not the same as "serious," which is based on patient/event outcome or action taken.

The investigator must determine the severity of each adverse event according to the National Cancer Institute CTCAE. For terms not specified with the CTCAE, the criteria in Table 7-1 should be used to determine the grade severity.

Table 7-1 Criteria for Determining the Grade/Severity of Adverse Event Terms Not Specified by the National Cancer Institute CTCAE

Grade	Criteria	
1/Mild	Asymptomatic or mild symptoms, clinical or diagnostic observations only; intervention not indicated	
2/Moderate	Minimal, local, or noninvasive intervention indicated; limiting age-appropriate instrumental activities of daily living	
3/Severe or medically significant	Not immediately life-threatening; hospitalization or prolongation of hospitalization indicated; disabling; limiting self-care activities of daily living	
4/Life-threatening	Life-threatening consequences; urgent intervention indicated	
5/Death	Death related to adverse event	

Adverse event severity should be recorded in the appropriate section of the adverse event case report form and in the patient's source documents.

7.5. Adverse Events of Clinical Interest Reporting

Adverse events of clinical interest in this study are defined as any increase in ALT or AST \geq 3 x ULN.

Any ALT or AST elevation of this degree or greater occurring during the open-label Treatment period or Safety Follow-up period should be reported to the sponsor using the Serious Adverse Event Form within 24 hours of the study site personnel's knowledge of the event (see Section 7.6), even if the event does not meet serious adverse event criteria. Additional instructions for evaluating patients with an increase in ALT or AST ≥ 3 x ULN may be found in Appendix 5.

7.5.1. Criteria for Temporary Withholding of Study Drug in Association with Liver Test Abnormalities

Hepatic enzymes will be monitored in accordance with FDA drug-induced liver injury guidelines [FDA, 2009].

If the following liver test abnormalities develop, study drug should be withheld immediately with appropriate clinical follow-up (including repeat laboratory tests, until a patient's laboratory profile has returned to normal/baseline status), and the event reported as a serious adverse event:

- ALT or AST $> 8 \times ULN$; or
- ALT or AST > 5 x ULN and persists for more than 2 weeks; or

- ALT or AST > 3 x ULN and total bilirubin > 2 x ULN or INR > 1.5; or
- ALT or AST > 3 x ULN with appearance of fatigue, nausea, vomiting, right upper quadrant pain or tenderness, fever, rash and/or eosinophilia (> 5%).

Rechallenge may be considered if an alternative cause for the abnormal liver tests (ALT, AST, total bilirubin) is discovered and the laboratory abnormalities resolve to normal or Week 52/Baseline values. The investigator and sponsor must discuss and agree with any decision to rechallenge.

Rechallenge should not occur when the etiology of the liver test abnormalities is considered possibly drug-induced.

7.5.2. Criteria for Permanent Discontinuation of Study Drug in Association with Liver Test Abnormalities

Study drug treatment should be discontinued permanently if all of the following 4 criteria are met (i.e., potential severe drug-induced liver injury/Hy's law case):

- 1. AST or ALT increases to ≥ 3 x ULN; AND
- 2. Total bilirubin increases to $> 2 \times ULN$ or INR > 1.5; AND
- 3. Alkaline phosphatase value does not reach 2 x ULN; AND
- 4. No alternative cause explains the combination of the above laboratory abnormalities; important alternative causes include, but are not limited to the following:
 - Hepatobiliary tract disease;
 - Viral hepatitis (e.g., hepatitis A/B/C/D/E, Epstein Barr virus);
 - Exposure to hepatotoxic agents/drugs or hepatotoxins, including herbal and dietary supplements, plants, and mushrooms;
 - Alcoholic hepatitis;
 - Nonalcoholic steatohepatitis;
 - Autoimmune hepatitis.

If an alternative cause for hepatotoxicity is identified, then it should be determined (based on the severity of the hepatotoxicity or event) whether study drug treatment should be withheld or permanently discontinued as appropriate for the safety of the patient.

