Approximately 360 patients completing the OLE study and meeting the definition of responder and meeting all other eligibility criteria will be randomized 1:1 to blinded treatment with oral relugolix with E2/NETA or placebo, once daily, for up to 52 weeks. Stratification variables will include geographic region (North America vs Europe vs Latin America vs Rest of World), duration of relugolix exposure prior to randomization (28 weeks vs 52 weeks), and baseline menstrual blood loss volume in the Parent study ($< 225 \text{ mL vs} \ge 225 \text{ mL}$). For patients whose menstrual bleeding returns to $\ge 80 \text{ mL}$ (heavy menstrual bleeding), treatment with open-label relugolix with E2/NETA (latter also referred to as "addback" in context of hormonal "add-back") will be restarted. A Schedule of Activities is provided in Table 1-1.

Screening and Baseline Procedures: The study consists of a screening period and a treatment period (randomized or open-label) of up to 52 weeks. Screening and baseline procedures will be done at the same visit for this Randomized Withdrawal study (referred to as the "Week 52/Baseline visit" in this study), which coincides with the Week 52 visit of the OLE study and will be defined as the date of completion of the last procedure in the OLE study (see Schedule of Activities; Table 1-1). The Week 52/Baseline visit will include vital signs, physical examination, laboratory assessments, a 12-lead electrocardiogram (ECG), bone densitometry, patient-reported outcome assessments, transvaginal ultrasound, and endometrial biopsy (only if required). When Week 52/Baseline procedures in the OLE study have been completed, the investigator will assess patient eligibility for participation in this study. The eligibility assessment will be based on data available at the Week 52/Baseline visit. No study

Effective: 13-August-2018

procedures will be performed until the consent form is signed. Patients will receive their last dose of study drug in the OLE study on the day of the Week 52/Baseline visit (as per the OLE study protocol). Following confirmation that the patient is eligible for this Randomized Withdrawal study and has provided informed consent to participate, the patient will be provided blinded study drug to begin dosing the following day. The first dose of study drug will be self-administered the next morning following the Week 52/Baseline visit.

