5. TREATMENTS

5.1. Treatments Administered

Approximately 360 patients completing the OLE study and meeting the definition of responder and meeting all other eligibility criteria will be randomized 1:1 to blinded treatment with oral relugolix with E2/NETA (relugolix with add-back) or placebo for up to 52 weeks.

- Group A: 52 weeks of oral relugolix with E2/NETA, once daily;
- Group B: 52 weeks of placebo relugolix plus a capsule of placebo estradiol/norethindrone acetate.

The placebo relugolix tablet is manufactured to match the relugolix tablet in size, shape, and color. The placebo capsule is designed to match the over-encapsulated estradiol/norethindrone acetate active product in size, shape, color, and odor.

After randomization, if the alkaline hematin analysis confirms the return of heavy menstrual bleeding (defined as menstrual blood loss of ≥ 80 mL) the patient will be offered retreatment at their next visit with open-label relugolix with add-back for the remainder of the treatment period. Descriptions of all study drugs are provided in Table 5-1.

Table 5-1 Description of MVT-601-035 Study Drugs

Name of Investigational Product	Blinded and Open-Label Relugolix	Relugolix Placebo	Blinded Estradiol / Norethindrone Acetate	Estradiol / Norethindrone Acetate Placebo	Open-Label Estradiol / Norethindrone Acetate
Formulation Description	Round film- coated pink tablet	Round film- coated pink tablet	A Swedish orange, over-encapsulated round film-coated white tablet with back-fill material	A Swedish orange capsule with placebo back-fill material	Round, white, biconvex, film- coated tablet
Dosage Form	Tablet	Tablet	Capsule	Capsule	Tablet
Unit Dose Strength	40 mg	0 mg	Estradiol 1.0 mg / Norethindrone acetate 0.5 mg	0 mg	Estradiol 1.0 mg / Norethindrone acetate 0.5 mg
Route of Administration/ Duration	Oral once daily for up to 52 weeks	Oral once daily for up to 52 weeks	Oral once daily for up to 52 weeks	Oral once daily for up to 52 weeks	Oral once daily for up to 52 weeks

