6.1. Schedule of Observations and Procedures

Assessments should be completed at the designated visit/time points as described in the Schedule of Activities (see Table 1-1). The study is divided into 2 periods: Treatment period (Table 1-1) and Safety Follow-up period. Unscheduled visits may occur as needed to evaluate patients.

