QTc Prolongation Negative Thorough QT/QTc clinical study.	Empiric exclusion of baseline QTcF > 470 msec in the Parent studies.	12-lead ECG at the Week 52/Baseline and Week 104/Early Termination visits, and as clinically applicable; withdrawal for QTcF > 500 msec.	
Hepatic Enzyme increases Isolated increases in hepatic transaminases have been observed in prior clinical studies. There have been no reported cases consistent with drug-induced liver injury including an increase in bilirubin. Abnormal liver test results are considered adverse events of clinical interest in this study.	Exclusion criteria for AST and ALT > 2 x the ULN; total bilirubin values > 1.5 x ULN.	Abnormal liver test results (AST or ALT > 3 x ULN) that develop during the Treatment period will be reported within 24 hours of study personnel awareness.	

Effective: 13-August-2018

Potential Risk of Clinical Significance	ential Risk of Clinical Significance Mitigation Strate	
	Impact on Eligibility	Monitoring and Withdrawal Criteria
Phospholipidosis Data from nonclinical studies in rats and monkeys showed histopathological changes consistent with PLD. PLD by itself is not adverse. No clinical evidence of relugolix-related PLD-associated toxicity has been observed nor was there a clinically meaningful increase in a biomarker of PLD assessed in phase 2 clinical studies.	Patients with significant underlying medical conditions are excluded.	Routine safety monitoring including laboratory assessments, ECGs, and assessment of adverse events, including any ophthalmologic adverse events, will be monitored during this study.
Metabolic Changes Metabolic changes (insulin resistance, dyslipidemia, and increased weight) with increased risk of diabetes are a potential risk of the hypoestrogenic state induced by relugolix.	Exclusion criteria for current medical history of cardiovascular disease in the Parent studies.	Fasting lipids and glucose will be monitored during the study.
Reproductive Toxicity	Premenopausal compliance with specified acceptable nonhormonal contraception; exclusion of pregnant and lactating women.	Pregnancy testing at each study visit; immediate withdrawal for pregnancy.

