Appendix 5. Assessment of Abnormal Liver Tests

Study drug treatment (blinded relugolix monotherapy or relugolix co-administered with estradiol/norethindrone acetate or placebo) should be withheld for any liver test abnormality listed in Section 7.5.1, pending investigation of alternative causes of liver injury. Follow-up should continue until the liver test abnormalities resolve to baseline.

Monitor liver tests per the applicable schedule in Appendix Table 1, and per the investigations in Appendix Table 2. If close monitoring is not possible, study drug should be withheld even if the results do not meet the criteria for withholding in Section 7.5.1.

The medical monitor should be contacted for questions regarding adequate follow-up tests and frequency of follow-up tests for a patient.

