9.1.8. Adverse Events of Clinical Interest

Adverse Events of clinical interest in the randomized withdraw study are defined as any increase in ALT or AST $\geq 3 \times$ ULN, which are reported as “Yes” for adverse events of clinical interest in the adverse event CRF. Adverse events of clinical interest will be summarized.

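### Protocol Section 7.5 ties the 24-hour ALT/AST report to an undefined open-label Treatment period, in conflict with Table 7-2: a minor wording error in a safety rule

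*Protocol*

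**What the plan says.** Section 7.5 of the protocol (Amendment 1) defines an adverse event of clinical interest as any ALT or AST increase to at least 3 x ULN, with no limit on period. Its next sentence asks for a report to the sponsor on the serious adverse event form within 24 hours, even when the event is not serious, for elevations "occurring during the open-label Treatment period or Safety Follow-up period". The version effective 11 July 2018 has the same phrase, and the Amendment 1 summary of changes does not mention it.

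The hepatic row of Table 7-2 (Section 7.10) reads: "Abnormal liver test results (AST or ALT > 3 x ULN) that develop during the Treatment period will be reported within 24 hours".

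On study periods, Section 6.1 says: "The study is divided into 2 periods: Treatment period (Table 1-1) and Safety Follow-up period". The synopsis describes "a treatment period (randomized or open-label) of up to 52 weeks". Section 5.1 says that once return of heavy bleeding is confirmed, "the patient will be offered retreatment at their next visit with open-label relugolix with add-back".

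Section 7.5.1 lists four liver patterns for which drug is withheld "and the event reported as a serious adverse event". Section 7.6 sets 24 hours for every serious adverse event.

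**The concern.** The trial is double-blind. All women begin on blinded relugolix with E2/NETA or blinded placebo, and a woman who keeps her response never receives open-label drug. A reporting duty attached to an open-label period, taken at its word, does not apply to the phase for which the trial was designed.

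Two sites could then act differently on the same result. With an isolated ALT of 4 x ULN on blinded drug, a site following Section 7.5 to the letter need not notify the sponsor within 24 hours, while a site following Table 7-2 must. The protocol does not say which text prevails. Table 7-2 itself records that isolated transaminase rises were seen in earlier studies, and the Section 7.5 report exists to catch such non-serious findings quickly.

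**Working it through.** The check is a comparison of texts. The plan states no figure to reproduce.

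**Step 1. Does the named period exist?** Section 6.1 has two periods, Treatment and Safety Follow-up. The synopsis makes the first one randomized or open-label. Section 5.1 confines open-label drug to retreatment. So the period named in Section 7.5 is not defined, and the only open-label treatment in the trial is retreatment.

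**Step 2. Where do Section 7.5 and Table 7-2 differ?**

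- Period: open-label treatment in Section 7.5; the whole Treatment period in Table 7-2.
- Threshold: at least 3 x ULN in Section 7.5; above 3 x ULN in Table 7-2.
- Safety Follow-up: named in Section 7.5; not named in Table 7-2.

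**Step 3. What is reported within 24 hours on blinded drug?** Here *isolated* means without bilirubin > 2 x ULN, INR > 1.5, the listed symptoms or eosinophilia > 5%, and not serious under Section 7.1.2.

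| ALT or AST on blinded drug | 7.5 alone | 7.5.1 with 7.6 | Table 7-2 |
|---|---|---|---|
| > 8 x ULN | no | yes | yes |
| > 5 x ULN for more than 2 weeks | no | yes | yes |
| > 3 x ULN with bilirubin > 2 x ULN or INR > 1.5 | no | yes | yes |
| > 3 x ULN with listed symptoms or eosinophilia > 5% | no | yes | yes |
| > 5 to 8 x ULN for 2 weeks or less, isolated | no | no | yes |
| > 3 to 5 x ULN, any duration, isolated | no | no | yes |
| exactly 3 x ULN, isolated | no | no | no |

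Without Table 7-2, the last three rows go unreported. With it, only the last row does. In Safety Follow-up, Section 7.5 applies in full, so the silence of Table 7-2 there leaves no hole.

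**Step 4. Which scheduled tests are concerned?** Table 1-1 places post-baseline laboratory tests at Weeks 64, 76 and 104 and at Safety Follow-up, so there are 4 panels. For a woman who never relapses, Weeks 64, 76 and 104 fall on blinded drug: 3 panels are outside the letter of Section 7.5 and 4 - 3 = 1 is inside. For a woman still on blinded drug at the Week 76 panel, at least 2 are outside. These are counts of panels, not of events. The documents give no rate of isolated elevations, and unscheduled or repeat tests are not counted.

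**Step 5. What did the sponsor intend?** The definition sentence in Section 7.5 has no period limit. SAP Section 9.1.8 has none either: "Adverse Events of clinical interest in the randomized withdraw study are defined as any increase in ALT or AST" to at least 3 x ULN. Appendix 5 describes the study drug to be withheld as "blinded relugolix monotherapy or relugolix co-administered with estradiol/norethindrone acetate or placebo", so it expects liver findings on blinded drug. That phrase names a monotherapy that this trial does not give, so it is weaker evidence than the other two. Together with Table 7-2, the texts point to coverage of the whole Treatment period.

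**The case against.** The best reply is that the protocol already covers blinded drug. Section 7.5 does not say that elevations on blinded drug need not be reported, Table 7-2 says that they will be, and a site can obey both. On that view *open-label* is a stray word in a sentence whose two periods otherwise match those of Section 6.1. Of the three differences, the threshold concerns a single value and the Safety Follow-up one has no effect when both texts are followed.

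Most of this stands, and it is why the point is minor. It does not make the wording right. Section 7.5 is the operative instruction: it gives the form, the clock and the recipient. Table 7-2 is a risk summary that names neither form nor recipient. A mandatory safety duty should not depend on a site noticing the second text and choosing it over the first.

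A reader might infer three stronger things that the documents do not support.

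- *That liver signals on blinded drug go unreported.* Step 3 shows otherwise: Sections 7.5.1 and 7.6 apply in any period, and Table 7-2 covers the rest above 3 x ULN.
- *That the planning responder rates (60% and 40% at Week 76) give the number of women on blinded drug.* They do not. Under Section 6.2 a woman who relapses stays on randomized drug until the day before the retreatment visit at her next menses. A non-responder at Week 76 can therefore still be on blinded drug when the Week 76 panel is drawn.
- *That the liver tables will undercount.* The SAP 9.1.8 summary uses the case report form flag, whose definition has no period limit, and SAP Table 16 is built from post-baseline laboratory results.

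**Conclusion.** Wrong as written, minor. Section 7.5 names a period that the protocol does not define and, read alone, excludes blinded treatment from a 24-hour safety report that Table 7-2 requires.

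The effect is confined to prompt and uniform sponsor notification of elevations that are isolated, outside Section 7.5.1 and not otherwise serious. Patient care does not depend on it: Appendix Table 1 requires repeat tests every 48 to 72 hours at 3 x ULN or more with normal bilirubin and INR. No endpoint, sample size or error rate is touched.

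This rests on two assumptions: that some sites would take Section 7.5 at its word, and that neither text overrides the other. How many events are affected cannot be said from the documents.

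**What to change.** In Section 7.5, replace the period clause with: *occurring during the Treatment period (randomized or open-label retreatment) or Safety Follow-up period*. In the hepatic row of Table 7-2, change the threshold to *>= 3 x ULN* and the period to *Treatment or Safety Follow-up period*.

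Make both edits with the next amendment. If treatment is still ongoing, a short letter can meanwhile point sites to the Table 7-2 wording, which already covers blinded drug. SAP Section 2.1 describes enrolment in the past tense and SAP Section 7.1 already uses pooled baseline data, so the opportunity may be limited or gone.

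The cost is two text edits and a letter, plus the IRB/IEC submission and approval that Section 10.2.1 requires, across approximately 240 planned sites. Bundling with another amendment keeps this small. No visit, test or data item is added.
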